Research Study Title: Physiological Augmentation of Mindfulness Meditation (PAMM)

Principal Investigators: [name]

Protocol Date: 10/29/2021

NCT Number: NCT02754557

Scientific Protocol

Research Study: Physiological Augmentation of Mindfulness Meditation (PAMM)

Principal Investigators: [name]

Date: 10/29/2021

Background

Specific Aims:

The purpose of the present study is to test the efficacy of implementing breath-focused mindfulness-based interventions (MBIs) to reduce symptoms of dissociation that are associated with posttraumatic stress disorder (PTSD). We will test this intervention in a low-income sample by training increased attention to physiological sensations and basic emotion regulation skills. Additionally, we are interested in whether attentional control can be enhanced in this population via physiological feedback. We propose to evaluate the effectiveness of a breath-focused mindfulness meditation augmented with physiological feedback. This feedback will be given via a vibrating device that will be placed on a participant's sternum that vibrates in proportion to their breathing. Because we are interested in how attention and emotion regulation skills may change as a result of treatment in a real-world setting, such as outpatient clinics of public hospitals, we propose minimal exclusionary criteria and flexible treatment plans.

Supporting Research:

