ineffective. We hope to achieve this through the implementation of mindfulness-based interventions for people with psychiatric disorders, particularly PTSD. More specifically, we will measure attentional control, physiological functioning, and dissociative symptoms pre- and post-intervention to assess the relative usefulness of breath-focused mindfulness in reducing feelings of detachment from the self and increasing emotion regulation skills in chronically traumatized individuals. Attention control and emotional regulation will be measured in 3 ways: 1) through a breath meditation task during psychophysiological assessment with EEG, 2) through neuropsychological and interoception tasks using functional magnetic resonance imaging (fMRI), and 3) through self-report measures. These approaches will allow the examination of our associations of interest using both objective and subjective measures of attention and focus to gain a better understanding of whether dissociative symptoms of PTSD and trauma may be enhanced through mindfulness-based interventions. The intervention will be conducted with a low-income, African American sample with PTSD and dissociation as a result of trauma.

Design

Sample:

Population

Participants will be a total of 110 women between the ages of 18 and 65, recruited from Grady Memorial Hospital, an inner-city hospital in downtown Atlanta, GA.

Inclusion/Exclusion

Inclusion into the study will be dependent upon 1) experience of at least one Criterion A trauma, 2) presence of current symptoms of PTSD that are significantly interfering with functioning, 3) an MDI depersonalization score of 7 and fulfilling at least two of the four CAPS subscale criteria (clinically significant re-experiencing, avoidance, alterations in mood and cognitions, hyperarousal), and 4) willingness to participate in the study. Actively psychotic and cognitively compromised individuals will be excluded, in addition to alcohol or substance dependence and imminent risk of physical violence to self or others. Those who are determined to be at imminent risk of harm to themselves or others will be referred to a more appropriate treatment.

Setting:

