During the pre-intervention assessment, participants will complete clinical, neuropsychological, and interoception measures as well as EEG, psychophysiology, and fMRI. This session will last approximately 60 minutes and the participant will be compensated \$50. Visits 2-5 will involve breath-focused meditation for both augmented and non-augmented groups and concurrent measurements of EEG and psychophysiology. During visits 6-7, the non-augmented group will continue breath-focused meditation, whereas the augmented group will receive tapering levels of feedback, such that no physiological feedback will be present by the end of each session. Visit 8 will require the participant to complete the same tasks and surveys

completed during the first visit, as well as the MRI scan. These intervention visits will last 50 minutes each and the participant will be compensated \$20 per session for up to 7 sessions. The one-month follow-up will include only relevant self-report measures. This session will last approximately 60 minutes and the participant will be reimbursed \$50. Finally, the second follow up visit will last approximately 2 hours; this session will include 2 computer tasks completed inside the MRI scanner and self-report questionnaires. Compensation in the amount of \$50 will be provided for this follow-up.

Google Voice texting, a free texting service will be used to assist in study retention. Participants can miss intervention sessions due to forgetting their appointment times and missing reminder calls. The use of this texting service will allow participants to receive text message reminders of their appointments in addition the reminder calls.

Reimbursement to participants will be given via e-gift card. Participants will be emailed the e-gift card following each visit. E-gift cards will be purchased through Emory Express.

Measures:

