We have designed this study to have a final sample of 80 participants. The sample size of 80 was determined using a power analysis. Power was calculated using theoretical maximum detectable effect sizes given our samples. The proposed design, involving 40 completers in the active intervention arm and 40 completers in the control arm will yield sufficient power to detect effects at $d > .5$ for Aim 1) effects of the intervention of $d > .6$ and Aims 2 and 3) change in mechanism within the active group ($d > .6$) and across groups ($d > .6$). Although 80 is the minimum number needed to achieve statistically significant effects for our conditions of interest, we will enroll a higher number (110) with the expectation of attrition for some of these individuals.

All electronic data will be secured via an Emory secure network and password protection. Data will be managed electronically using REDcap. All participant data will be de-identified and all participants will be given a subject ID. Data gathered at each session will then be entered into REDcap with previous data and a hard copy of all data will be saved in a participant's folder. All hard copy data will be secured by storing it in a de-identified folder in a locked office in a locked

filing cabinet. Documentation regarding each session will also be kept as a hard copy in a participant's folder after being signed by both study researcher and licensed supervisor.

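### The first stated purpose, efficacy of breath-focused mindfulness on dissociation, has no control in this design; the two arms can show only what the vibration feedback adds.

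*Combined protocol and SAP*

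**What the plan says.** Background, Specific Aims, gives the purpose first as to "test the efficacy of implementing breath-focused mindfulness-based interventions (MBIs) to reduce symptoms of dissociation". The same paragraph then adds, as a further interest, the augmentation question: "We propose to evaluate the effectiveness of a breath-focused mindfulness meditation augmented with physiological feedback".

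The Significance section says that symptoms will be measured before and after the intervention "to assess the relative usefulness of breath-focused mindfulness in reducing feelings of detachment from the self".

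Under Procedure both groups meditate. "Visits 2-5 will involve breath-focused meditation for both augmented and non-augmented groups", and "During visits 6-7, the non-augmented group will continue breath-focused meditation" while feedback is tapered in the augmented group. No arm without meditation is described.

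Entry (Inclusion/Exclusion) requires "an MDI depersonalization score of 7 and fulfilling at least two of the four CAPS subscale criteria". No scale range, norm or SD is given for the score of 7.

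Data Analysis bases the sample size on a design "involving 40 completers in the active intervention arm and 40 completers in the control arm". For Aims 2 and 3 it names "change in mechanism within the active group" (d > .6) alongside a difference across groups (d > .6). The planned models are group x time, both for imaging and for PTSD symptoms, MDI and mindfulness.

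**The concern.** The purpose and the comparison do not match. A contrast between two meditating arms cancels whatever meditation itself does and leaves only the contribution of the vibration. If the first purpose is to be answered at all, the answer must come from change over time, either within one arm or as the time main effect of the mixed model.

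That change has no control. Participants enter with current, interfering symptoms, which may fluctuate or improve without treatment. They are also selected on MDI depersonalization and CAPS criteria, and the MDI and CAPS are outcomes. Nothing in Data Analysis confines efficacy conclusions to the interaction, and neither natural course nor regression to the mean is discussed. At stake is whether a fall in dissociation seen in both arms could be presented as evidence that breath-focused mindfulness works.

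**Working it through.** **1. What each quantity estimates.** Write the mean pre-to-post change as T + M in the non-augmented arm and T + M + V in the augmented arm. T is change that would occur anyway (natural course, regression, retesting), M the effect of meditation and V the effect of feedback.
- Group x time: (T + M + V) − (T + M) = V, if T is the same in both arms.
- Within the augmented arm: T + M + V.
- Time main effect with equal arms: T + M + V/2.

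No contrast in the design isolates M.

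**2. The plan's own figures.** The plan gives 40 completers per arm but neither a power percentage nor the sidedness of the test, so 80 cannot be strictly reproduced. At two-sided 5%, 40 per arm gives 61% power at d = .5 and 76.5% at d = .6 (normal approximation). The effect detectable with 80% power is (1.960 + 0.842) × √(2/40) = 0.63 between arms, and (1.960 + 0.842)/√40 = 0.44 for a paired test in one arm (d there in SDs of the change). A paired test has 96% power at d = .6. The within-arm test therefore reaches significance more easily, but it measures T + M + V.

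**3. How large T could be for the MDI, if the screening score is also the baseline.** The cut c (in SDs above the source-population mean) and the retest correlation r are assumptions; the documents give neither. With bivariate normal scores, entry at x ≥ c and no effect of any kind:

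expected fall = (1 − r) × φ(c) / [1 − Φ(c)]

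The ratio φ(c)/[1 − Φ(c)] is 0.798, 1.141 and 1.525 at c = 0, 0.5 and 1. Example: c = 0.5 and r = .7 give 0.3 × 1.141 = 0.34 SD. Each cell shows the fall in SD and the simulated chance of a significant fall in one arm of 40 (paired t-test, two-sided 5%).

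| c | r = .6 | r = .7 | r = .8 | r = .9 |
|---|---|---|---|---|
| 0 | 0.32; 65% | 0.24; 51% | 0.16; 37% | 0.08; 19% |
| 0.5 | 0.46; 92% | 0.34; 83% | 0.23; 64% | 0.11; 36% |
| 1 | 0.61; 99.6% | 0.46; 97% | 0.31; 87% | 0.15; 58% |

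The nominal rate in that direction is 2.5%. A t-test of change between the arms, on the same simulated data, rejects in about 5% of trials in every cell; the simulated arms are exchangeable by construction.

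**4. The same, if baseline is a separate measurement.** Let screening, baseline and post scores all correlate r with each other. Baseline and post then have the same expected value given the screening score, so the expected fall is r × φ(c)/[1 − Φ(c)] − r × φ(c)/[1 − Φ(c)] = 0. Rejection is 5% two-sided, about 2.5% as a fall, whatever c and r. If the screening-to-post correlation is instead midway between r and r², total rejection is about 8% to 25%.

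**5. The within-active-group mechanism test.** Entry does not select on connectivity, EEG or interoception. Regression reaches such a measure only through its correlation q with the selection variable. Over the same grid, with the screening-time value as baseline, the chance of a significant shift in the regressing direction is about 2.5% at q = 0, 5% to 24% at q = .3 and 8% to 57% at q = .5. Separately, tasks are repeated: the Affective Number Stroop is done in the scanner before and after treatment. If practice alone moved a measure by an assumed paired d of 0.2 to 0.4, 40 participants would give significance in 23% to 69% of trials.

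**The case against.** The strongest reply is that the trial is already an augmentation study. Its title says so, the Specific Aims include "We propose to evaluate the effectiveness of a breath-focused mindfulness meditation augmented with physiological feedback", Supporting Research predicts higher theta activity with augmentation than without, and the word relative in the Significance sentence can be read as comparative. Data Analysis plans group x time models and no stand-alone pre-post test of the MDI. All of this is correct. It shows that the analysis suits the second aim. It does not supply a control for the first, which stands in the opening sentence as the purpose.

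Three stronger readings are tempting, and the documents do not support them.
- A reader might infer that a null intervention would almost certainly be reported as reducing dissociation. The plan does not say that efficacy will be claimed from a time effect. The high rates in step 3 also need the screening MDI to serve as baseline. Recruitment and Procedure describe an eligibility interview, and Measures has the self-report scales given at pre-intervention. This suggests a separate baseline without settling it.
- A reader might apply those rates to the within-active-group test for Aims 2 and 3. That test concerns mechanism, not dissociation, so they do not carry over. Such a test can be a legitimate check that the intervention engages its target, and the plan does not call it evidence of efficacy.
- A reader might treat group x time as safe without condition, or conversely conclude that the arms were not randomized. The documents describe random selection of people in waiting rooms and say nothing on how participants are allocated to arms. Neither inference is warranted.

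**Conclusion.** The point stands as a mismatch between stated purpose and design. The efficacy of breath-focused mindfulness on dissociation has no control; only the increment from physiological feedback does. This part follows from the text and needs no assumption.

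The size of the possible artefact in the MDI is uncertain. With no true effect, one arm of 40 would show a significant fall in about 19% to more than 99% of trials if screening doubles as baseline, against nominal error if a separate baseline has equal retest correlations. Both figures rest on assumed cuts of 0 to 1 SD and retest correlations of .6 to .9. That the score of 7 marks raised dissociation is itself an inference. Outcome scoring on the MDI as a whole, with selection on one subscale, could weaken the effect. A separate baseline does not remove confounding with natural course. For mechanism measures the exposure is to practice and time effects, and to regression only through correlation with the selection variables.

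**What to change.** - **Specific Aims and Significance:** restate the purpose as the incremental effect of physiological feedback over the same breath-focused meditation.
- **Data Analysis, sample size:** label within-active-group mechanism change as a descriptive check of target engagement, not evidence of efficacy. It need not be deleted.
- **Data Analysis, models:** state that efficacy conclusions come only from the group x time contrast, not from within-arm change or the time main effect.
- **Supporting statements:** say how participants are allocated to arms, since the contrast is protected only if the arms are comparable, and whether the baseline MDI is measured separately from the eligibility MDI.

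These are wording changes; they need no new participants or procedures. The cost is a narrower claim. Keeping the first purpose as a controlled question would need an arm without meditation, which is a different trial.

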The interventions will take place at the Glenn Building on Grady Hospital Campus. The Glenn Building is an Emory building where all of our research offices are located on the basement level. The interventions will occur at an EEG recording booth. The pre- and post-interventions, including MRI scans, will be completed at Wesley Woods Health Center on the Emory University campus and the Georgia Tech/Georgia State University Center for Advanced Brain Imaging (CABI).

Recruitment:

Participant identification and recruitment will follow several steps. First, participants will be randomly selected from people sitting in the waiting rooms of the primary care clinics, diabetes, and obstetric/gynecologist clinics of Grady Memorial Hospital. This selection process is for participation in the Grady Trauma Project (IRB00002114 and IRB00009375). Only women will be recruited in this setting and they will be recruited in the same manner as at Grady

Hospital, by randomly selecting people sitting in the waiting room and asking them if they would be interested in participating in the Grady Trauma Project. If the participant is consented and participates in the Grady Trauma Project and during the course of his or her participation is found to be exhibiting serious untreated (or under-treated) symptoms of PTSD or depression as a result of trauma, our study will be briefly described, and participants will be given the option of whether or not to allow a study coordinator to contact them. The participants may have the option to be consented electronically via REDcap. Agreeing to be contacted does not require agreeing to participate in the study. If a participant expresses interest in this study, agrees to be contacted, and provides contact information, a study researcher will contact him or her by phone to assess whether the participant is still interested and to set up an initial clinical interview to determine appropriateness for the study.

We will also recruit people from the community, including treatment-seeking individuals (such as patients at the Emory Clinic). A study flyer, containing basic information on study requirements and exclusions, was created to assist in participant recruitment. This flyer will be distributed to the community via social media and to the Emory Clinic as well as Grady Hospital.

Procedure:

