Once participants express interest in the study, a study coordinator will contact them to assess whether they are still interested and administer a brief phone screen to confirm eligibility. The phone screen will ask about general physical health, identify potential contraindications of having an MRI scan, and assess if the participant is experiencing any PTSD symptoms. The interviewer will assess potential PTSD symptoms using the Modified PTSD Symptom Scale (MPSS) and the Primary Care PTSD Screen (PC-PTSD) (described more in depth in the measures section). If the participant is deemed eligible after the phone screen, they will be scheduled for an initial interview. The interview will be conducted by trained research assistants and will ask more in depth questions regarding psychiatric symptoms and life experiences.

If participants agree to be in the study and are determined to be appropriate for inclusion, they will begin to meet with their study clinician twice a week for three weeks after an initial assessment. A follow-up assessment will be conducted one month after the participant's treatment to examine any gains in attention, mindful focus, and interoceptive ability. To further assess any residual effects of the study intervention, an additional follow-up MRI session will be conducted between 1 month to 5 years after the final intervention session; this session will include additional assessments related to attention, learning, and subjective feedback about the intervention. The participants will receive instructions on a computer screen on how to conduct breath-focused mindfulness. Additionally, they will complete functional magnetic resonance imaging (fMRI) scans during the first session and the second follow-up session. Continuous EEG and psychophysiology data will also be collected during sessions 1-7. If participants are dissatisfied, they may withdraw from the study at any time.

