PSS. The PTSD Symptom Scale (PSS (Foa et al., 1993) is an 18-item self-report measure that assesses the presence and severity of PTSD symptoms related to specific traumatic events in individuals with a known trauma history. PTSD symptomatology over the prior 2 weeks is assessed, yielding a continuous measure of PTSD symptom severity ranging from 0 to 51.

Kentucky Mindfulness Scale. The Kentucky Mindfulness Scale is a 39-item scale that assesses skills related to what one does while practicing mindfulness. This is measured based on the following criteria: 1) Noticing or attending to current experience, 2) describing the experience with words, 3) participating in the activity, 4) being accepting and non-judgmental, 5) using undivided attention, and 6) being effective.

Multidimensional Assessment of Interoceptive Awareness. This is a clinical measure that assesses various aspects of interoception, including ability to attend to body sensations, regulate distress by attending to body sensations, and experiencing body sensations as safe and trustworthy.

Kreek-McHugh-Schluger-Kellogg scale. This is a clinical measure designed to quickly assess the nature and extent of recreational substance use, including opioids, alcohol, tobacco, and cannabis. It assesses frequency, amount and duration of exposure to each substance during the person's period of greatest use and in the past 30 days. The full measure will be administered at the beginning of study participation, and one question about drug use in the past day (if applicable) will be administered on study intervention days.

Affective Number Stroop task. In this Affective Number Stroop (ANS) task, participants are instructed to rapidly identify the number of numbers in a given display while ignoring evocative distractor images (trauma-relevant scenes). In these trials, the number of numbers presented is either consistent or inconsistent with the actual number displayed, such that there are both congruent and incongruent trials. The participants will be presented with positive and neutral pictures in addition to the negative trauma-relevant images. The task will be completed in the MRI scanner during both the pre- and post-treatment sessions. This task is meant to evoke the attentional problems that many GTP participants encounter while performing daily tasks by engaging attentional control resources and including images that are relevant to participants' traumas.

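### Does the Procedure section's list of fMRI sessions leave the pre-post imaging analysis without a post-treatment scan?

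*Combined protocol and SAP*

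**What the plan says.** The Procedure section describes scanning twice. Its general account says that participants "they will complete functional magnetic resonance imaging (fMRI) scans during the first session and the second follow-up session". The same paragraph places a first follow-up at one month after treatment and then adds that "an additional follow-up MRI session will be conducted between 1 month to 5 years after the final intervention session", with the stated purpose "To further assess any residual effects of the study intervention".

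The next paragraph goes visit by visit. It includes fMRI in the pre-intervention assessment. At Visit 8 the participant repeats the tasks and surveys "completed during the first visit, as well as the MRI scan". For the visit after that, "The one-month follow-up will include only relevant self-report measures". For the second follow-up, "this session will include 2 computer tasks completed inside the MRI scanner and self-report questionnaires".

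Two other places bear on the schedule. The Setting section states: "The pre- and post-interventions, including MRI scans, will be completed at Wesley Woods Health Center" (with a second imaging centre also named). The Affective Number Stroop entry under Measures states: "The task will be completed in the MRI scanner during both the pre- and post-treatment sessions".

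The Data Analysis section tests group by time (pre-post) on voxel-wise activity and on mean connectivity. Connectivity is examined in two conditions: incongruent Stroop trials and the rumination condition of the Rumination task. No visit number is attached to post.

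**The concern.** On a first reading, the general account lists the scan occasions and leaves out the end of treatment. The one-month visit cannot supply the missing scan, because the visit-by-visit account restricts it to questionnaires. If the list were complete, the first scan after baseline would be the late one, at any point from 1 to 60 months after the last session.

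That would matter for the imaging analysis. A pre-post contrast with so wide a window would mix an immediate effect of augmentation with whatever persisted, or happened, over as much as five years. It would also lose a condition: the tasks named for the late visit are the Stroop and Visual Statistical Learning, so rumination connectivity would have no scan after baseline. Because the Stroop is scanned at the late visit too, an analyst could in principle take either scan as post.

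**Working it through.** The plan gives no figure to reproduce here. The check is to set each statement about scanning beside the others.

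| Source | First session | Visit 8 / post-treatment | One month | Late follow-up |
|---|---|---|---|---|
| Procedure, general account | scan | not listed | not listed | scan |
| Procedure, visit by visit | scan | scan | self-report only | scan, 2 tasks |
| Setting | scan | scan | silent | silent |
| Measures, Stroop entry | scan | scan | silent | silent |

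**Step 1: which visit is the second follow-up?** The general account puts one follow-up at one month and then an additional MRI session. The visit-by-visit account uses the label second follow-up for the visit with in-scanner tasks that comes after the one-month visit. So it is the late session, and its window runs from 1 month to 5 × 12 = 60 months.

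**Step 2: count the occasions.** The general account names {first session, second follow-up} = 2. The visit-by-visit account names {pre-intervention, Visit 8, second follow-up} = 3. The difference is one entry, Visit 8.

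**Step 3: contradiction or omission?** Both occasions in the general account are correct under the visit-by-visit account. The sentence does not say that they are the only ones. The same paragraph calls the late session additional, which fits a scan added to a pre-post pair. Three of the four sources in the table place a scan at the end of treatment, and none denies one.

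**Step 4: does each connectivity condition have a post scan?** Visit 8 repeats the first-visit tasks and adds the MRI. The Stroop entry confirms the Stroop explicitly. The Rumination task is covered as a first-visit task repeated at Visit 8. Conditions with a Visit 8 scan: 2 of 2. The loss of rumination arises only if the visit-by-visit account is accepted for the one-month and late visits but ignored for Visit 8, and nothing justifies that selection.

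**Step 5: which visit is post?** For clinical outcomes the Data Analysis section uses pre, post and follow-up as three separate levels. For imaging it uses pre and post only. With the terms used consistently, post is the end-of-treatment visit and the late scan is a follow-up. The stated purpose of the late session, residual effects, agrees with this. So does the rumination condition, which could not be analysed pre-post from the late visit's named tasks.

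**The case for a change.** The strongest case for a change is practical. Staff schedule visits from the Procedure section, and an end-of-treatment scan that is missed cannot be obtained later. Two Stroop scans after baseline exist by design, and the Data Analysis section neither says which one enters the model nor describes an analysis of the late one. The Visual Analogue Scale entry under Measures refers to the last MRI session after the intervention, which could mean either visit. Naming the visit would cost a few words and would remove a choice from the analyst.

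Much of this is accurate as description. The sentence is incomplete, the post visit is not numbered, and the scale's timing is loosely worded. There is a further loose end: the opening of the Measures section gives the behavioural tasks at the one-month session as well, whereas the Procedure section limits that session to self-report. Neither place puts a scan there, so the imaging schedule is unaffected.

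The consequence does not follow. A coordinator using the Procedure section meets the Visit 8 scan in the next paragraph, in the only account organised by visit. An analyst who needs a post value for both conditions has one visit that provides it. No passage proposes using the late scan in place of a missing Visit 8 scan, so a rule against doing so would guard against something the plan does not contemplate. The Data Analysis section specifies no analysis of the Visual Analogue Scale.

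**Conclusion.** The concern identifies a real slip of wording: one of three scan occasions is missing from one sentence. It does not identify a defect in the design or analysis. The remaining text already supplies the end-of-treatment scan, gives both connectivity conditions a post value, and separates post from follow-up. Completing the sentence or numbering the post visit would be tidy if the protocol were being edited for another reason, but neither would alter what is collected, tested or concluded. The planned 80 completers, the enrolment of 110 and the stated detectable effects do not depend on it.

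This rests on three readings: that the visit-by-visit paragraph is the operating schedule; that the second follow-up is the late session in both paragraphs; and that the Rumination task is among the scanned first-visit tasks repeated at Visit 8, which the pre-post connectivity analysis presupposes. The text supports each of them, and nothing in it points the other way.
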